16.3 Assessment of Acute Kidney Injury

Acute kidney injury will be staged if KDIGO criteria for either serum creatinine or urine output are met:

Stage	Serum creatinine	Urine output
1	1.5-1.9x increase from baseline	<0.5 ml/kg/h for 6-12 hours
	OR absolute increase of 26.5 micromol/L	
2	2.0-2.9x increase from baseline	<0.5 ml/kg/h for >12 hours
3	3.0 x increase from baseline OR increase in serum creatinine to 353.6 micromol/L OR need for renal replacement therapy	<0.3 ml/kg/h for > 24 hours OR Anuria > 12 hours

16.4 Assessment of Delirium

Delirium should be assessed using the 4AT score and will be considered to be present if $4AT \ge 4$ (see Appendix C).

IRAS 299977/308830

Version 5.0 26Jun2024

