1.4.2 Secondary Endpoints

Secondary outcomes at 30 days are as follows:

- 1. All-cause mortality
- 2. New Myocardial Injury post-randomisation (New MINS)
- 3. Individual MACE components (including type of arrhythmia)
- 4. Complications (including AKI, infection, delirium)
- 5. Proportion of participants transfused; volume of blood transfused per patient
- 6. Discharge destination (home, other hospital, nursing home, other)
- 7. Acute hospital length of stay
- 8. ED-5D-5L

Additional secondary outcomes at 120 days are as follows:

- 1. All cause mortality
- 2. Secondary care costs
- 3. Unplanned hospital readmissions
- 4. Mobility (as defined by NHFD or SHFA dataset
- 5. Residential status (as defined by NHFD or SHFA dataset)
- 6. EQ-5D-5L
- 7. Health services resource use

Clinical outcomes will be measured until acute hospital discharge or 30 days post randomisation whichever is soonest. Death, readmission, mobility, residential status, quality of life and resource use will be measured at 120 days post-randomisation.

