4.2.3 Consent for people without capacity

Some people may be unable to give informed consent because of pain, delirium, or cognitive impairment. This may be temporary, but in the case of people with dementia, loss of capacity may be permanent. Elderly adults with hip fracture are a patient group with a high rate of incapacity both from pre-existing cognitive impairment and/or because of the acute injury. Hip fracture and the associated pain and requirement for analgesia also contribute to a high prevalence of delirium, which can also impair mental capacity. Identification of the contribution of pre-existing and acute incapacity is extremely challenging and may not be possible in a high proportion of cases. However, it is vital to include people with both pre-existing and acute incapacity, or a mixed picture, in the trial to ensure its relevance and generalisability. It is also

CR007-T02 v0.5 Page **27** of **69**

IRAS 299977/308830

Version 5.0 26Jun2024

biologically plausible that the intervention could modify acute incapacity due to delirium, which is an important secondary outcome.

Eligible participants who are assessed as lacking capacity to consent will be enrolled in the study in accordance with the legal requirements of that part of the devolved nations where recruitment is taking place. Consequently, different processes will apply in different UK devolved administrations, and a flow-chart describing this is provided in APPENDIX E.

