5.2.2 Other study interventions

Participants pre-consented to take part in RESULT-Hip but not yet randomised

All participants enrolled in RESULT-Hip will have their haemoglobin and U&Es (urea and electrolytes) measured as per local practice. This must include a measurement preoperatively and on the first and second postoperative days at a minimum. Additional blood sampling will be at the discretion of the clinical team

Participants randomised to the study intervention (both arms)

All participants randomised to RESULT-Hip will have their haemoglobin and U&Es (urea and electrolytes) measured as per local practice. We would expect participating sites to measure Haemoglobin pre-operatively and, on the first, and second post-operative days as part of routine care.

Haemoglobin and U&Es will be measured at randomisation (baseline) and once more in days 2 - 5. Blood samples for troponin analysis (analysis to take place in Edinburgh, results not available to clinical team) will be taken at randomisation (baseline) and then twice more in days 1 to 5, ideally on the 1st and 3rd calendar days after randomisation with all samples being at least 24h apart from each other. The baseline sample should be taken as soon as possible after randomisation (on the same day and ideally within 4 hours of randomisation). ECGs will be performed at baseline and repeated once in days 2 - 5.

If it is anticipated that the participant will be discharged before Day 3, these assessments should be carried out pre-discharge.

CR007-T02 v0.5 Page **32** of **69**

IRAS 299977/308830

Version 5.0 26Jun2024

Haemoglobin will also be measured as soon as possible after every transfusion given as part of the study (ideally within 24 hours).

Additional blood sampling will be at the discretion of the clinical team unless Haemoglobin is not measured as part of routine care for 5 consecutive days. The protocols for blood sampling and measurement in each study site will be checked and clarified during site set-up.

4AT assessment will be carried out at randomisation, and then twice more in days 1 to 5, ideally on the 1st and 3rd calendar days after randomisation.

EQ-5D-5L will be measured at randomisation, or as soon as practicable after, and at days 30 +/- 7 days and at day 120 +/- 7 days.

Health services utilisation will be measured by questionnaire at 30 +/- 7 days and 120 +/- 7 days.

IRAS 299977/308830

Version 5.0 26Jun2024

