7 DATA COLLECTION

7.1 DATA COLLECTION

The following data will be collected from participants in RESULT-Hip.

Screening Data

Anonymised screening data will be recorded on screening logs and entered onto the database by research teams at site. This data will be used to generate a CONSORT diagram at the end of the trial

At enrolment (pre-consent)

- Participant Name
- Participant Contact details
- Personal Consultee Name and Contact details (if appropriate)
- date of admission
- Date of birth

At Randomisation:

- Age
- Gender
- Pre-existing cardiovascular disease
- haemoglobin

At Baseline or as soon as available afterwards.

- CHI or NHS number
- ethnicity (using British Census 2021 categories)
- residential status (own home/sheltered housing, residential care, nursing care)
- pre-fracture mobility status (see NHFD proforma APPENDIX D)
- Abbreviated Mental Test Score (AMTS) or AMT4
- fracture type (see NHFD proforma APPENDIX D)
- date of surgery
- ASA-PS
- type of anaesthesia (general, spinal, other regional)
- operation performed
- duration of surgery
- preoperative haemoglobin
- haemoglobin after surgery (PACU, Recovery Ward, Ward on operative day)
- number of allogeneic units of blood transfused intraoperatively
- G number as a record of all red cell transfusions administered
- Use of blood sparing management technology or therapies
- history of dementia
- pre-existing malignancy
- pre-existing cardiovascular disease

CR007-T02 v0.5 Page **36** of **69**

IRAS 299977/308830

Version 5.0 26Jun2024

- cardiovascular risk factors (vascular disease, diabetes, hypertension, kidney disease)
- presence of atrial fibrillation
- cardiac medications
- anticoagulant and anti-platelet medications
- Creatinine and eGFR
- Troponin
- 12-lead electrocardiogram
- Nottingham Hip Fracture Score (33)
- Rockwood Clinical Frailty Scale
- 4 'A's Test (4AT) for delirium
- EQ-5D-5L

Post randomisation the following will be collected:

- Haemoglobin and U&E's, one measurement days 2 5. Where possible these will be timed with existing blood sampling.
- pre and post transfusion haemoglobin (each transfusion episode, according to transfusion guidelines)
- Two blood samples for troponin for batch analysis in Edinburgh
- ECG on the 3rd day (window day 2 5) following randomisation
- Number of units of blood transfused following first time of Hb less or equal to 90 g. L⁻¹
- Volume of blood transfused (ml) following first time of Hb less or equal to 90 g. L⁻¹

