18 APPENDIX C – DELIRIUM ASSESSMENT USING 4AT

[1] ALERTNESS

This includes patients who may be markedly drowsy (e.g., difficult to rouse and/or obviously sleepy during assessment) or agitated/hyperactive. Observe the patient. If asleep, attempt to wake with speech or gentle touch on shoulder. Ask the patient to state their name and address to assist rating.

Normal (fully alert, but not agitated, throughout assessment)	0
Mild sleepiness for <10 seconds after waking, then normal	0
Clearly abnormal	4

[2] AMT4

Age, date of birth, place (name of the hospital or building), current year.

No mistakes	0
1 mistake	1
2 or more mistakes/untestable	2

[3] ATTENTION

Ask the patient: "Please tell me the months of the year in backwards order, starting at December." To assist initial understanding one prompt of "what is the month before December?" is permitted.

Months of the year backwards	Achieves 7 months or more correctly	0	
	Starts but scores <7 months / refuses to start		1
	Untestable (cannot start because unwell, drowsy, inattentive)		2

[4] ACUTE CHANGE OR FLUCTUATING COURSE

Evidence of significant change or fluctuation in: alertness, cognition, other mental function (e.g., paranoia, hallucinations) arising over the last 2 weeks and still evident in last 24hrs

	No Yes	0 4
4 or above: possible delirium +/- cognitive impairment		

1-3: possible cognitive impairment

0: delirium or severe cognitive impairment unlikely (but delirium still possible if [4] information incomplete)

GUIDANCE NOTES

[figure not shown]
Version 1.2. Information and download: www.the4AT.com

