The 4AT is a screening instrument designed for rapid initial assessment of delirium and cognitive impairment. A score of 4 or more *suggests* delirium but is not diagnostic: more detailed assessment of mental status may be required to reach a diagnosis. A score of 1-3 suggests cognitive impairment and more detailed cognitive testing and informant history-taking are required. A score of 0 does not definitively exclude delirium or cognitive impairment: more detailed testing may be required depending on the clinical context. Items 1-3 are rated *solely on observation of the patient at the time of assessment*. Item 4 requires information from one or more source(s), e.g., your own knowledge of the patient, other staff who know the patient (e.g., ward nurses), GP letter, case notes, carers. The tester should take account of communication difficulties (hearing impairment, dysphasia, lack of common language) when carrying out the test and interpreting the score. 4AT SCORE

Alertness: Altered level of alertness is very likely to be delirium in general hospital settings. If the patient shows significant altered alertness during the bedside assessment, score 4 for this item. AMT4 (Abbreviated Mental Test - 4): This score can be extracted from items in the AMT10 if the latter is done immediately before. Acute Change or Fluctuating Course: Fluctuation can occur without delirium in some cases of dementia, but marked fluctuation usually indicates delirium. To help elicit any hallucinations and/or paranoid thoughts ask the patient questions such as, "Are you concerned about anything going on here?"; "Do you feel frightened by anything or anyone?"; "Have you been seeing or hearing anything unusual?"

© 2011-2014 MacLullich, Ryan, Cash

IRAS 299977/308830

Version 5.0 26Jun2024

Patient ID / Hospital number

Κ

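### Section 16.4 calls delirium present at any 4AT of 4 or more without using the baseline 4AT, so new onset and persistence are merged and an effect on new delirium is diluted

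*Protocol*

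**What the plan says.** Delirium is named among the complications in the 30-day secondary endpoints (Protocol 1.4.2), and 4.2.3 calls it an important secondary outcome. Appendix A, which defines the complications, gives the rule in 16.4: "Delirium should be assessed using the 4AT score and will be considered to be present if" the score is 4 or more. It does not require the delirium to be new and does not mention baseline.

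The schedule in 5.2.2 provides a baseline value: "4AT assessment will be carried out at randomisation, and then twice more in days 1 to 5". Section 7.1 lists "4 'A's Test (4AT) for delirium" and "history of dementia" among the baseline data, and adds case-note review to the post-randomisation 4AT.

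On the population, 4.2.3 expects delirium to be common and says "it is vital to include people with both pre-existing and acute incapacity, or a mixed picture, in the trial". It also says that the intervention could plausibly modify incapacity due to delirium.

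Appendix C reads the cut-off more cautiously than 16.4 does: "4 or above: possible delirium +/- cognitive impairment". Its guidance notes say that such a score suggests "delirium but is not diagnostic: more detailed assessment of mental status may be required to reach a diagnosis".

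**The concern.** A complication of a transfusion strategy should be distinguishable from a condition that preceded allocation. Under 16.4 it is not. A participant delirious at randomisation and still delirious on day 1 is counted in the same way as one who becomes delirious on day 3.

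Neighbouring outcomes are handled differently. The creatinine criteria for AKI in 16.3 are mainly rises from baseline, and the troponin component of the primary outcome in 1.4.1 is restricted to new MINS.

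If many participants are positive at baseline and treatment does not alter their course, they add the same number of events to each arm. The overall rate rises, the risk ratio moves towards 1 and power falls. Because the rule mixes onset with persistence, neither a null nor a positive result shows which of the two was affected.

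**Working it through.** The protocol states no delirium rate, effect size or power, so there is no figure of its own to reproduce.

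**Step 1: which pre-existing states meet the rule (Appendix C scoring).** Alertness scores 0 or 4, AMT4 0 to 2, attention 0 to 2, acute change 0 or 4.

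- Acute change alone gives 4. It covers a change that arose in the previous two weeks and is still evident in the last 24 hours. Follow-up 4ATs fall on days 1 to 5, so the two-week window always reaches back before randomisation, and unresolved earlier delirium scores 4.
- With normal alertness and no acute change, only one combination reaches 4: AMT4 = 2 and attention = 2. Attention scores 2 only if untestable. A person who starts but does poorly, or refuses to start, scores 1, for a total of at most 3.

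**Step 2: dilution.** From the protocol: 507 evaluable per arm and a two-sided 5% level (section 9.1, set for the primary outcome and borrowed here). Assumed: new-onset rate p = 20% control and 14% liberal (risk ratio 0.70) among those with baseline 4AT below 4; share positive at baseline b = 10%, 20%, 30%; share of those still positive afterwards s = 100%. The rule is read as any post-randomisation 4AT of 4 or more.

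Observed rate = b·s + (1 − b)·p. For b = 20%: 0.20 + 0.80 × 0.20 = 36.0% and 0.20 + 0.80 × 0.14 = 31.2%, so the ratio is 0.312/0.360 = 0.87.

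Power = Φ[(d − 1.96·SE0)/SE1], with SE0 = √(2·p̄(1 − p̄)/n) and SE1 = √([pC(1 − pC) + pT(1 − pT)]/n).

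- Rule as written, b = 20%, n = 507: d = 0.048, SE0 = 0.02967, SE1 = 0.02963. Φ[(0.048 − 0.05815)/0.02963] = Φ(−0.34) = 37%.
- New cases only, n = 507 × 0.80 = 405.6: d = 0.060, SE0 = 0.02638, SE1 = 0.02629. Φ[(0.060 − 0.05170)/0.02629] = Φ(0.32) = 62%.

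| Positive at baseline | Rates under 16.4 | Risk ratio | Power, 16.4 | Power, new only (n per arm) |
|---|---|---|---|---|
| 10% | 28.0% vs 22.6% | 0.81 | 51% | 68% (456) |
| 20% | 36.0% vs 31.2% | 0.87 | 37% | 62% (406) |
| 30% | 44.0% vs 39.8% | 0.90 | 27% | 57% (355) |

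With new onset of 15% or 25%, s of 60% or 100% and b of 10% to 40%, a true ratio of 0.70 appears as 0.76 to 0.95. The power lost against new-only is about 9 to 32 points.

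**Step 3: treatment also shortens existing delirium.** Take b = 20%, new onset 20% vs 14%, and control persistence 80%, so the control rate is 0.20 × 0.80 + 0.80 × 0.20 = 32.0%. New-only power is 62% throughout.

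| Persistence, liberal arm | Liberal rate | Power, 16.4 |
|---|---|---|
| 80% (no effect) | 27.2% | 39% |
| 72% | 25.6% | 61% |
| 68% | 24.8% | 72% |
| 56% | 22.4% | 93% |

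**Step 4: any delirium, stratified by baseline 4AT.** The strata are weighted (1 − b) and b: difference = (1 − b)·d0 + b·d1, variance = (1 − b)²·V0 + b²·V1. At b = 20%, power is 63% against 37% unstratified when all baseline cases persist, 52% against 39% when persistence is 80% in both arms, and 97% against 93% when it falls from 80% to 56%.

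**The case against.** The strongest reply is that 16.4 gives only a cut-off for a single assessment. It does not say how the two follow-up scores combine, and the use of baseline 4AT could be settled in the SAP, which is not shown. Part of this stands: adjustment or stratification belongs there and would recover power. But 16.4 sits in the appendix that defines the complications, and an adjusted analysis would not change who counts as a case.

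The morbidity survey in 16.1 uses the word new in its neurological row, and that could be read as covering delirium. It is a separate instrument and the wording is ambiguous. It does not qualify the 4AT rule.

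Any delirium after randomisation is also a legitimate outcome. Comparing it between randomised arms is valid, and restricting to baseline-negative participants sets aside people whom 4.2.3 wants included. This stands. If treatment speeds resolution, a new-only outcome can be the weaker one (62% against 93% in Step 3). New-only should therefore not be the sole definition.

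A reader might infer that stable dementia in general is recorded as delirium. Appendix C does not support that: without altered alertness or acute change, only someone with AMT4 of 2 who is untestable on attention reaches 4.

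**Conclusion.** The point holds as a defect of definition in one secondary outcome. Section 16.4 merges new delirium with delirium that preceded randomisation, and with one severe form of stable impairment, although the baseline 4AT that would separate new from pre-existing cases is collected.

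If treatment acts only on new delirium, the effect is diluted: 0.70 appears as 0.81 to 0.90, with power of 51% to 27% against 68% to 57%. These figures rest on the assumed rates, on full persistence of baseline cases and on the borrowed 507 per arm.

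A reader might go further and infer that the rule biases the comparison or hides any treatment effect. The documents do not support that. Allocation is randomised, so baseline cases balance in expectation, and the effect is attenuated rather than removed. Section 4.2.3 also leaves open an effect on existing delirium, under which the loss relative to new-only shrinks or reverses. The primary outcome and the sample size are untouched.

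**What to change.** In 16.4, define new delirium as a baseline 4AT below 4 followed by any post-randomisation 4AT of 4 or more. For participants with a baseline 4AT of 4 or more, report persistence or resolution separately. Keep the any-delirium comparison in all randomised participants, stratified by or adjusted for baseline 4AT, and carry the same wording into the SAP before database lock.

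No new data are needed. The cost is one more reported breakdown and a smaller denominator for the new-onset result. Because the any-delirium comparison is retained, an effect on existing delirium is not lost.

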17 APPENDIX B – SERIOUS ADVERSE TRANSFUSION RELATED EVENTS

Definitions of transfusion related SAEs are per the NHS Blood and Transplant "Serious Hazards of Transfusion" (SHOT) available at

http://www.shotuk.org/wp-content/uploads/SHOT-Definitions-Jan-2016-1.pdf

Expected Red Blood Cell Transfusion reactions

Acute transfusion reactions (ATR) are defined (SHOT Report, 2012) as those occurring at any time, up to 24 hours following a transfusion of blood or components.

- Anaphylactic reactions
- Moderate allergic reactions
- Hypotensive reactions
- Severe febrile reactions
- Mixed febrile/allergic reactions
- incorrect component being transfused
- haemolytic reactions
- transfusion-related acute lung injury (TRALI)
- transfusion-associated circulatory overload (TACO)
- transfusion-associated dyspnoea (TAD)
- bacterial contamination

IRAS 299977/308830

Version 5.0 26Jun2024

18 APPENDIX C – DELIRIUM ASSESSMENT USING 4AT

[1] ALERTNESS

This includes patients who may be markedly drowsy (e.g., difficult to rouse and/or obviously sleepy during assessment) or agitated/hyperactive. Observe the patient. If asleep, attempt to wake with speech or gentle touch on shoulder. Ask the patient to state their name and address to assist rating.

Normal (fully alert, but not agitated, throughout assessment)	0
Mild sleepiness for <10 seconds after waking, then normal	0
Clearly abnormal	4

[2] AMT4

Age, date of birth, place (name of the hospital or building), current year.

No mistakes	0
1 mistake	1
2 or more mistakes/untestable	2

[3] ATTENTION

Ask the patient: "Please tell me the months of the year in backwards order, starting at December." To assist initial understanding one prompt of "what is the month before December?" is permitted.

Months of the year backwards	Achieves 7 months or more correctly	0	
	Starts but scores <7 months / refuses to start		1
	Untestable (cannot start because unwell, drowsy, inattentive)		2

[4] ACUTE CHANGE OR FLUCTUATING COURSE

Evidence of significant change or fluctuation in: alertness, cognition, other mental function (e.g., paranoia, hallucinations) arising over the last 2 weeks and still evident in last 24hrs

	No Yes	0 4
4 or above: possible delirium +/- cognitive impairment		

1-3: possible cognitive impairment

0: delirium or severe cognitive impairment unlikely (but delirium still possible if [4] information incomplete)

GUIDANCE NOTES

[figure not shown]
Version 1.2. Information and download: www.the4AT.com

The 4AT is a screening instrument designed for rapid initial assessment of delirium and cognitive impairment. A score of 4 or more *suggests* delirium but is not diagnostic: more detailed assessment of mental status may be required to reach a diagnosis. A score of 1-3 suggests cognitive impairment and more detailed cognitive testing and informant history-taking are required. A score of 0 does not definitively exclude delirium or cognitive impairment: more detailed testing may be required depending on the clinical context. Items 1-3 are rated *solely on observation of the patient at the time of assessment*. Item 4 requires information from one or more source(s), e.g., your own knowledge of the patient, other staff who know the patient (e.g., ward nurses), GP letter, case notes, carers. The tester should take account of communication difficulties (hearing impairment, dysphasia, lack of common language) when carrying out the test and interpreting the score. 4AT SCORE

Alertness: Altered level of alertness is very likely to be delirium in general hospital settings. If the patient shows significant altered alertness during the bedside assessment, score 4 for this item. AMT4 (Abbreviated Mental Test - 4): This score can be extracted from items in the AMT10 if the latter is done immediately before. Acute Change or Fluctuating Course: Fluctuation can occur without delirium in some cases of dementia, but marked fluctuation usually indicates delirium. To help elicit any hallucinations and/or paranoid thoughts ask the patient questions such as, "Are you concerned about anything going on here?"; "Do you feel frightened by anything or anyone?"; "Have you been seeing or hearing anything unusual?"

© 2011-2014 MacLullich, Ryan, Cash

IRAS 299977/308830

Version 5.0 26Jun2024

Patient ID / Hospital number

Κ

